D. Adverse event reporting.....	27
X. REFERENCES.....	28

ABBREVIATIONS

1,25D = 1,25-dihydroxyvitamin D

25D = 25-hydroxyvitamin D

AKI = Acute Kidney Injury

APACHE = Acute Physiology and Chronic Health Evaluation

AUC = Area Under the Curve

BWH = Brigham and Women's Hospital

CKD = Chronic Kidney Disease

DSMB = Data safety and monitoring board

HED = Human Equivalent Dose

ICU = Intensive Care Unit

ESRD = End Stage Renal Disease

MCT Oil = Medium Chain Triglyceride Oil

NIDDK = National Institute of Diabetes and Digestive Kidney Diseases

NIH = National Institutes of Health

PBMC = Peripheral Blood Mononuclear Cells

PHRC = Partners Human Research Committee

RCT = Randomized Controlled Trial

RRT = Renal Replacement Therapy

SCr = Serum creatinine

SOFA = Sequential Organ Failure Assessment

ULN = Upper limit of normal

TRIAL SUMMARY

Title

Activated Vitamin D for the Prevention and Treatment of Acute Kidney Injury (ACTIVATE-AKI)

Objective

To assess the efficacy of calcifediol (25-hydroxyvitamin D [25D]) and calcitriol (1,25-dihydroxyvitamin D [1,25D]) in preventing and reducing the severity of acute kidney injury (AKI) in critically ill patients.

Hypothesis

Compared to placebo, treatment with calcifediol or calcitriol will reduce the occurrence and severity of renal injury, as determined by a composite of time-averaged daily serum creatinine (SCr) levels for 7 days, renal replacement therapy (RRT), and death.

Study Design

ACTIVATE-AKI is a 3-arm, randomized, double-blind, placebo-controlled, phase II trial (n=150) of vitamin D metabolites in critically ill patients at risk of severe AKI. We will randomly assign participants in a 1:1:1 fashion to receive calcifediol, calcitriol, or placebo. Study drugs will be administered on a daily basis for 5 days, and will be administered either orally or via naso/orogastric tube.

Study Sites

ACTIVATE-AKI is a single-center study that will recruit patients from intensive care units at Brigham and Women's Hospital (BWH).

Funding

ACTIVATE-AKI is approved and funded by the National Institutes of Health (NIH) / National Institute of Diabetes and Digestive Kidney Diseases (NIDDK) grant K23DK106448 (to [name]).

Registration on clinicaltrials.gov

NCT02962102

I. BACKGROUND AND SIGNIFICANCE

[figure not shown]
A. Historical background

Overview of AKI

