Inclusion Criteria	Exclusion Criteria

 • Age \geq 18 • Admitted to the ICU within 48h prior to enrollment • Likely to remain in the ICU (alive) for \geq72h • Naso/orogastric tube or ability to swallow • High risk of severe AKI* 	
 • Total serum calcium > 9.0 mg/dl or phosphate > 6.0 mg/dL within previous 48h • Currently receiving oral calcium supplementation • Ingestion of vitamin D₃ >1,000 IU/day or any 25D or 1,25D during the previous 7 days • AKI stage 2 or 3 (based on SCr and/or UOP criteria) • History of transplantation or chronically (>7days) receiving immunosuppressive medications (not including glucocorticoid steroids at a dose \leq prednisone 20 mg/day) • Neutropenia (<1000 PMNs/mm³) in the previous 48h • Primary parathyroid disease (active), granulomatous disease (active), or symptomatic nephrolithiasis in the previous 3 months • Receiving cytochrome P450 inhibitors[†] • CKD stage V or ESRD • Hgb < 7 g/dL • GI malabsorption • Prisoner • Pregnant or breastfeeding • Enrolled in a conflicting study, including any study with a research blood draw

Table 2. Inclusion and Exclusion Criteria. *Patients are considered to be at high risk of severe AKI if they have either: AKI stage 1, defined as an increase in SCr \geq 0.3 mg/d within the previous 48 hours, \geq 50% within the previous 7 days, or urine output \leq 0.5 ml/kg/h x 6 hours); or if they have an AKI risk score \geq 6 – see Table 3. [†]Patients will be excluded if they are receiving any of the following medications: ketoconazole, atazanavir, clarithromycin, indinavir, itraconazole, nefazodone, nelfinavir, ritonavir, saquinavir, telithromycin, or voriconazole, since these drugs may inhibit enzymes involved in vitamin D metabolism.

Risk Factor	Points
Chronic	
Age > 70y	1
Hypertension	1
Diabetes Mellitus	2
Chronic Liver Disease (cirrhosis, NAFLD, AIH, or chronic viral hepatitis)	2
Congestive Heart Failure (NYHA class 3 or 4)	2
Chronic Kidney Disease (baseline eGFR < 60 ml/min/1.73m ²)	3
Acute	
Blood pH (venous or arterial) \leq 7.30	2
Sepsis	2
Mechanical ventilation expected to last > 24 hours	2
Hypotension/shock, defined as MAP < 70 mm Hg or use of pressors/inotropes	2

Table 3. AKI Risk Prediction Score

B. Source of Subjects

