Participants will be randomly assigned, in a 1:1:1 fashion, to receive calcifediol, calcitriol, or placebo. Randomization will be stratified by the presence or absence of AKI on enrollment, defined by an increase in serum Cr ≥ 0.3 mg/dl within the previous 48 hours, $\geq 50\%$ within the previous 7 days, or urine output ≤ 0.5 ml/kg/h x 6 consecutive hours during any 6-hour block in the previous 24 hours. Randomization will be performed by the BWH research pharmacy using a computer generated sequence and permuted blocks.

V. STUDY PROCEDURES

A. Parameters to be measured

Clinical data

Upon enrollment in the study, the following demographic variables will be recorded: age, gender, race, ethnicity, comorbidities, active medications, active medical issues, reason for ICU admission, date of ICU/hospital admission, ICU location (e.g., MICU, CCU), and severity of illness at the time of study enrollment, as measured by APACHE II and SOFA scores.

In addition, the following clinical outcomes data will be recorded:

- ICU-, hospital-, and 28-day mortality
- ICU and hospital length of stay
- Incidence/severity of new/worsening AKI (defined by KDIGO guidelines)⁸⁸ within 1 week of enrollment
- Duration of mechanical ventilation
- Duration of vasopressor support
- Daily Sequential Organ Failure Assessment (SOFA) scores for the first 7 days of the study
- Physiologic data including heart rate, blood pressure, oxygenation, and urine output during the first 7 days of the study
- Hypocalcemia requiring I.V. calcium replacement during the first 7 days of the study
- Total serum calcium levels on a daily basis for the first 7 days of the study

28-day mortality

[figure not shown]
For patients discharged from the hospital prior to day 28, investigator [name]. will ascertain 28-day survival by calling the patient and/or their surrogate 28 days after enrollment as a courtesy follow-up to thank them for participating and to answer any questions they may have. The duration of the phone call is expected to last less than 2 minutes.

Blood samples

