Primary end point. The primary end point is a composite of renal injury, RRT, and death. Renal injury will be assessed by time-averaged (area under the curve [AUC]) levels of daily SCr for the first 7 days following enrollment. This end point has been used in previous clinical trials conducted in AKI,⁸⁹ and these measurements will be obtained through routine clinical testing. To account for missing data, we will standardize the AUC of daily SCr levels relative to the number of days in which SCr data are available. RRT and death are important confounders of SCr levels, as well as important end points by themselves, and will therefore be considered along with the AUC of SCr levels as part of the primary composite end point. RRT will be defined as receipt of any form of dialysis within the first 7 days of enrollment. Death will be defined as all-cause mortality within the first 7 days of enrollment.

To evaluate the primary composite end point, which includes both continuous (SCr levels) and dichotomous (RRT and death) variables, we will use a rank-based procedure, as prior studies have done,⁹⁰ as follows:

- Patients who die within 7 days of enrollment will be assigned the highest (worst) rank, with no difference in rank assigned to patients who die at different times within the first 7 days.
- Patients who survive >7 days but who require RRT within 7 days of enrollment will be assigned the second highest rank.
- All other patients will be assigned a rank based on the AUC of their SCr, as described above.

Secondary end points. Secondary end points will include new or worsening AKI (defined by KDIGO guidelines);⁹¹ kidney function on hospital discharge (assessed by SCr); hospital- and ICU length of stay; and hospital-, ICU-, and 28-day mortality. We will also evaluate the AUC of urinary injury biomarkers, including KIM-1, NGAL, and IL-18, during the first 5 days using a similar global rank score strategy as described above. Finally, we will evaluate organ-failure free days (assessed by daily SOFA scores) during the first 7 days following enrollment. For the cardiovascular component of the SOFA score, we will use a modified scoring system that has improved accuracy in predicting outcomes,⁹² and for the renal component we will assign a score of “4” (the highest score) to any participant who requires RRT.

C. Statistical methods

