To evaluate the primary end point, we will compare the ranks between treatment groups versus the placebo group with the use of the Wilcoxon Rank Sum test. To evaluate secondary end points, we will compare means and medians between each of the active treatment groups versus the placebo group using parametric (e.g., t-test) and non-parametric (e.g., Wilcoxon Rank Sum) tests, as appropriate. To account for two active treatment groups, we will consider p values <0.025 to be significant for the primary end point. For secondary end points, all of which will be considered exploratory, we will consider p values <0.05 to be significant.

D. Power analysis

150 participants (N=50 per group) will provide >80% power to detect a 0.62 standard deviation difference in the global rank score in each of the active treatment groups vs. placebo, with a two-sided α of 2.5%.

VII. RISKS AND DISCOMFORTS

A. Complications of surgical and non-surgical procedures

Not applicable

B. Drug side effects and toxicities

The only known toxicity of vitamin D metabolites, including calcifediol and calcitriol, is hypercalcemia.^{81 82} Despite an excellent safety profile, transient hypercalcemia has been reported with calcitriol and, to a much lesser extent, with calcifediol. The risks of hypercalcemia in the current study are low, since the planned doses of calcifediol and calcitriol are lower than doses that have been used safely in prior studies in humans (discussed in detail in sections 1E and 1F). Additionally, the following precautions will further minimize risk to patients:

1) Limiting our study to patients with serum total calcium levels ≤ 9.0 mg/dl. Most prior clinical studies of calcifediol and calcitriol (discussed in sections 1E and 1F) were conducted in patients who were generally normocalcemic on enrollment. In contrast, most ICU patients have serum calcium levels in the low-normal range, and many patients (55.2% in one study)⁹³ are frankly hypocalcemic on arrival to the ICU. In the current study, we will exclude patients with serum total calcium levels > 9.0 mg/dl on enrollment (**Table 2**). By limiting enrollment to patients with serum total calcium levels ≤ 9.0 mg/dl, a substantial barrier exists for serum calcium levels to rise into the hypercalcemic range (>10.7 mg/dl) and an even larger barrier for clinically relevant hypercalcemia (>11.5 mg/dl).

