Loss of confidential patient information is a potential risk in any clinical trial. To minimize this risk we will collect our database only on partners-protected computers; we will not include any protected health information in our primary database or in any study documents; the key linking the patient's study ID# with their name and medical record number will be kept in a separate folder on a partners-protected computer. The key linking the treatment group with the study ID will be kept on a separate password-protected computer by the BWH research pharmacy. Biological specimen tubes containing plasma and urine will be tagged with study ID#'s only and will not include any protected health information. Specimens will be stored in locked freezers at Brigham and Women's hospital.

Storing of genetic samples

Genetic samples will be stored in locked freezers at Brigham and Women's Hospital and kept for a maximum of 25 years. The samples will be labeled with a study ID only; no protected health information will be shared with collaborators outside of Partners. Genetic data will not be placed onto publicly available repositories such as the National Institutes of Health (NIH) central repository.

D. Device complications/malfunctions

Not applicable

E. Psychosocial risks

Not applicable

F. Radiation risks

Not applicable

VIII. POTENTIAL BENEFITS

A. Potential benefits to participating individuals

Individuals receiving calcifediol or calcitriol may derive benefit through the drug's actions on immune/inflammatory pathways that are directly involved in the pathogenesis of AKI. Our hypothesis that these pharmacologic agents may prevent/attenuate AKI in critically ill patients is supported by ample data from preclinical studies and preliminary data in humans (discussed in detail in section I).

B. Potential benefits to society

Potential benefits to society include elucidation of the physiology of vitamin D metabolism in critically ill patients. Moreover, this study will help answer important questions about mechanisms responsible for the association between vitamin D deficiency and adverse outcomes, including AKI, in critically ill patients. Understanding whether the immune/inflammatory response can be enhanced by calcifediol or calcitriol will inform the research community whether a larger study of either agent, powered to evaluate hard end points such as mortality, is justified.

IX. MONITORING AND QUALITY ASSURANCE

A. Independent monitoring of source data

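### Two optional efficiency gains in VI.C: analyse the primary end point by the AKI stratum used in randomisation, and replace the fixed 0.025 per comparison with Holm

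*Combined protocol and SAP*

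**What the plan says.** Section IV.C: "Randomization will be stratified by the presence or absence of AKI on enrollment", with 1:1:1 allocation in permuted blocks.

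Section VI.B builds one ranking across all patients. Deaths within 7 days share the worst rank and survivors who need RRT share the next. For the rest: "All other patients will be assigned a rank based on the AUC of their SCr, as described above".

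Section VI.C: "we will compare the ranks between treatment groups versus the placebo group with the use of the Wilcoxon Rank Sum test". No stratum or covariate is named, so the test is read as unstratified. For the two active arms, "we will consider p values <0.025 to be significant for the primary end point". No stepwise rule is given.

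Section VI.D claims more than 80% power with 50 per group "to detect a 0.62 standard deviation difference in the global rank score in each of the active treatment groups vs. placebo", at a two-sided 2.5%.

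**The concern.** Stratified randomisation balances the arms on AKI status. A pooled rank test still counts the difference between strata as noise. Its standard error is then too large, its true error rate falls below the nominal 2.5%, and power is lost.

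AKI at enrolment could well be prognostic: it is defined partly by a rise in SCr, and the end point ranks SCr over 7 days. The link may nevertheless be modest. AKI stages 2 and 3 are excluded, patients without AKI qualify through a risk score of at least 6 in which CKD carries the most points, and the end point uses absolute SCr, which CKD also raises.

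The fixed 0.025 is a separate matter. It controls family-wise error, but once one drug has succeeded the other could be tested at 0.05 without exceeding 5% overall.

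Section I.G says a benefit on AKI would support a larger trial, and VIII.B, in a sentence about the immune response, asks "whether a larger study of either agent, powered to evaluate hard end points such as mortality, is justified". With 50 per arm and little spare power, missing a real effect of the second drug, or of either drug, has a cost.

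**Working it through.** **The plan's own figure.** Inputs from VI.D: n = 50 per arm, 0.62 SD, two-sided 2.5%. The expected z is 0.62 × √(50/2) = 3.10 and the critical value is 2.241. Power = Φ(3.10 − 2.241) = 80.5%, so the stated figure reproduces. It is 79.4% with the t distribution. A Wilcoxon test with tied death and RRT ranks gave about 77% in simulation.

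**Part 1: the stratum.** Let R² be the share of rank variance explained by AKI. With arms balanced within strata, the stratified statistic has the same numerator as the Wilcoxon but a within-stratum variance, so z grows by 1/√(1−R²). In the normal approximation:

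- pooled type I error = 2 × [1 − Φ(2.241/√(1−R²))]
- pooled power = Φ((3.10 − 2.241)/√(1−R²))
- stratified power = Φ(3.10/√(1−R²) − 2.241)

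For AKI share p and a gap of g latent SDs between AKI and no AKI, R² is approximately p(1−p)g²/(1 + p(1−p)g²). With p = 50% (assumed):

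| Gap g | R² | Pooled type I error | Pooled power | Stratified power |
|---|---|---|---|---|
| 0 | 0 | 2.5% | 80.5% | 80.5% |
| 0.25 | 1.5% | 2.4% | 80.7% | 81.1% |
| 0.5 | 5.9% | 2.1% | 81.2% | 83.0% |
| 1.0 | 20% | 1.2% | 83.1% | 89.0% |

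Simulation of the actual end point used 40,000 trials per scenario. Assumptions: 50% AKI, 12% death and 8% RRT on placebo, blocks of 6, and a shift set so that the mean rank difference is 0.62 within-arm rank SD. The Monte Carlo error is about 0.2 points for power. The same pattern appears from a lower base:

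| Gap | Type I error, pooled | Power, pooled | Power, stratified on global ranks |
|---|---|---|---|
| 0 | 2.5% | 77.4% | 77.4% |
| 0.25 | 2.3% | 77.4% | 77.8% |
| 0.5 | 2.1% | 77.9% | 79.8% |
| 1.0 | 1.2% | 79.6% | 86.4% |

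The stratified test held 2.4 to 2.5% type I error throughout. With 30% or 70% AKI the gains at gaps 0, 0.5 and 1.0 were 0, 1.6 and about 6 points.

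The trial's title is "Activated Vitamin D for the Prevention and Treatment of Acute Kidney Injury", so the effect may differ between strata. Change in power against the pooled test, in points, at gaps 0 / 0.25 / 0.5 / 1.0:

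| Where the effect lies | Stratified on global ranks | van Elteren |
|---|---|---|
| AKI patients only | +3.3 / +1.4 / +0.1 / +0.7 | −1.0 / −3.5 / −5.1 / −4.2 |
| Three times larger in AKI | +0.7 / 0.0 / +0.2 / +3.1 | −0.6 / −1.5 / −1.2 / +2.1 |
| Patients without AKI only | +3.5 / +6.3 / +9.1 / +12.4 | not tabulated |

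Van Elteren re-ranks within strata and can lose power; the test on the plan's own ranks did not lose more than 0.05 points in any of the 42 scenarios run.

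**Part 2: Holm.** The fixed rule spends 2 × 0.025 = 5%. With the shared placebo arm (correlation 0.5), the actual family-wise error is 4.65% under either rule. Normal theory, both drugs at 0.62 SD, 2,000,000 draws:

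| | Fixed 0.025 | Holm |
|---|---|---|
| At least one significant | 91.6% | 91.6% |
| Both significant | 69.4% | 78.4% |
| Per comparison | 80.5% | 85.0% |

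The last row is the mean of the first two: (91.6 + 69.4)/2 = 80.5 and (91.6 + 78.4)/2 = 85.0. In no draw did the fixed rule reject where Holm did not.

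With the pooled Wilcoxon at gap 0, per-comparison power goes from 77% to 82%, both significant from 65% to 75%, and at least one stays at about 89%. With the drugs at 0.62 and 0.31 SD, power for the weaker one goes from 23% to 32%. If only one drug works, the gain is about 0.2 points and the inactive arm's false-positive rate rises from about 2.4–2.6% to 4.1–4.3%.

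**Together.** Family-wise error is 4.6% at gaps 0, 0.5 and 1.0. At gap 0.5 with both drugs working, per-comparison power is 78% as planned and 84% with both changes.

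**The case against.** The plan contains no error: test, multiplicity control and power are all prespecified, and the power figure reproduces. The gain from stratifying rests on two quantities the documents do not give, and their own eligibility rules suggest a modest link. At gaps of 0.25 and 0.5 with equal effects the gain is only 0.4 and 1.9 points; the large figures need a 1.0 SD gap or a benefit confined to patients without AKI. Holm does not raise the chance that at least one drug succeeds, and a stricter threshold for each arm is a defensible choice in phase II, where it is unknown which metabolite is better.

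All of this stands as a limit on the size of the gain, and it is why both changes are optional. It does not show a reason to ignore the stratum: the stratified test on global ranks cost nothing measurable in the scenarios run. For Holm there is a real trade-off, the higher false-positive rate for an inactive arm when the other drug works, and the investigators may weigh it differently.

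The objection also rightly asks which patients are ranked (the 100 in a comparison or all 150) and which AKI classification is used. A check found the same pattern with either rank set, but the plan should state both.

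**Conclusion.** The point holds as a recommended improvement, not a correction. The unstratified Wilcoxon is valid and conservative if AKI is prognostic.

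Stratifying gains nothing if AKI is not prognostic and the effect is the same in both strata, about 2 points at a 0.5 SD gap and about 7 at 1.0 SD. This assumes 50% AKI, 12% death, 8% RRT and a 0.62 SD effect on the within-arm rank scale; effect patterns outside the scenarios run were not checked. If 0.62 is read as a pooled rank SD, baseline power is 82% and Holm takes it to 87%.

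That Holm rejects at least as much as the fixed rule at the same 5% family-wise error needs no assumption about AKI. Its benefit, about 5 points per comparison, arises when both drugs work and goes to the second one.

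**What to change.** Amend VI.C before unblinding. Either change can be made without the other.

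1. **Stratified test.** Keep the VI.B ranking across both strata, with midranks for ties. For each active arm against placebo, use a Cochran-Mantel-Haenszel mean-score test on those ranks, stratified by AKI at enrolment. The statistic is the active-arm rank sum minus its within-stratum expectation. Its variance is the sum over strata of (n_active × n_placebo / N) times the sample variance of the ranks in that stratum, which handles ties. State the rank set; ranking the 100 patients in each comparison keeps the Wilcoxon numerator when arms are balanced. State that the stratum is the one recorded at randomisation. Keep the unstratified Wilcoxon as a sensitivity analysis. Avoid van Elteren as the default: it loses about 0.5 points when AKI is not prognostic and the effect is equal, and 3.5 to 5 points at gaps of 0.25 to 1.0 when only AKI patients benefit.
2. **Holm.** Test the smaller p value at 0.025 and, only if it is significant, the other at 0.05.

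The cost is two or three sentences, with no new data, patients or procedures. The one statistical price is the Holm trade-off: an inactive arm's false-positive rate of 4.1–4.3%, still below 5%, when the other drug works.

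### The fixed 0.025 threshold for both primary comparisons is valid, but a Holm step-down would give the second comparison more power within the same 5% family-wise bound

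*Combined protocol and SAP*

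**What the plan says.** Section IV.C sets up three equal arms: "Participants will be randomly assigned, in a 1:1:1 fashion, to receive calcifediol, calcitriol, or placebo". For the primary composite rank, section VI.C says "we will compare the ranks between treatment groups versus the placebo group with the use of the Wilcoxon Rank Sum test". The multiplicity rule follows in the same section. It opens with its reason, "To account for two active treatment groups", and then sets the threshold: "we will consider p values <0.025 to be significant for the primary end point".

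Section VI.D uses the same per-comparison level, two-sided 2.5%: "150 participants (N=50 per group) will provide >80% power to detect a 0.62 standard deviation difference in the global rank score", and this applies "in each of the active treatment groups vs. placebo".

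The plan describes no step-down, hierarchical or Dunnett-type procedure and gives no reason for preferring a fixed split. It does not write down a family-wise level; 5% is inferred from 2 × 0.025. Section VI plans no confidence intervals.

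**The concern.** Under the fixed rule, a drug whose p value falls between 0.025 and 0.05 is declared negative even when the other drug has already succeeded. At that point the implied 5% error budget would allow the second drug to be tested at 0.05.

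The second comparison matters in this trial. Section I.C presents the three-arm design as the way to resolve uncertainty about which metabolite works in patients, and section VIII.B says the results will inform whether a larger study of either agent is worth doing. A candidate could be set aside on a threshold stricter than the error bound requires.

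**Working it through.** **Inputs.** 50 per arm, effect 0.62 SD, two-sided α 0.025 per comparison (VI.D); Wilcoxon rank sum test of each active arm against placebo (VI.C); 1:1:1 allocation (IV.C). With equal arms and a shared placebo, the two test statistics have a correlation of about 0.5.

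**1. Reproduce the plan's power.** Normal approximation: the test statistic has mean 0.62 × √(50/2) = 3.10, and the critical value at two-sided 0.025 is 2.241. Power = Φ(3.10 − 2.241) = 80.5%, and the required size is 50 per arm. The stated >80% reproduces. At two-sided 0.05 the critical value is 1.960, and stand-alone power is Φ(3.10 − 1.960) = 87.3%.

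**2. Where the two rules differ.** Holm tests the smaller p value at 0.025 and, if that is significant, the other at 0.05.
- Neither p value below 0.025: both rules reject nothing.
- Both below 0.025: both rules reject both.
- One below 0.025, the other 0.05 or more: both rules reject one.
- One below 0.025, the other from 0.025 to below 0.05: the fixed rule rejects one, Holm rejects both.

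Only the last case differs. Whether at least one comparison succeeds is therefore always the same under both rules.

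**3. Error bound.** If neither drug works, any false claim needs a p value below 0.025, with probability at most 0.025 + 0.025 = 0.05. If exactly one drug is inactive, a false claim needs its own p value below 0.05, with probability at most 0.05. Neither step assumes independence, so the shared placebo arm is no obstacle.

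**4. Gain by normal approximation, 0.62 SD in both arms, correlation 0.5.**
- P(both statistics exceed 2.241) = 0.694.
- P(one exceeds 1.960 and the other exceeds 2.241) = 0.739.
- Holm per comparison = 0.805 + 0.739 − 0.694 = 85.0%, against 80.5% under the fixed rule.
- Holm for both drugs = 2 × 0.739 − 0.694 = 78.4%, against 69.4%.
- At least one drug = 2 × 0.805 − 0.694 = 91.6% under both rules.

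**5. Gain with the planned test.** Simulated three-arm trials, 50 per arm, Wilcoxon tests, normally distributed data with a location shift. The normal shift is an assumption. Each cell shows fixed 0.025 → Holm.

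| True effects (SD) | Per arm | Both arms rejected | At least one rejected |
|---|---|---|---|
| 0.62 and 0.62 | 77.0% → 82.0% | 64.5% → 74.7% | 89.4%, unchanged |
| 0.62 and 0.31 | stronger 76.7% → 77.4%; weaker 22.6% → 31.1% | 21.2% → 30.4% | 78.1%, unchanged |
| 0.31 and 0.31 | about 22–23% → 25–26% | about 10% → 16% | unchanged |
| 0.62 and 0 | active 77.0% → 77.2%; inactive 2.4% → 4.1% | 1.5% → 3.4% | 77.9%, unchanged |
| 0 and 0 | 2.4% → 2.6% | 0.3% → 0.7% | 4.4%, unchanged |

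In the last row, the 4.4% is the family-wise error when neither drug works; the normal approximation gives about 4.7%.

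**The case against.** The strongest case for leaving the text alone has four parts.

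**The rule is already sound.** It is prespecified, gives its reason, controls error and matches the power statement. A reader might infer from this point that VI.C contains a mistake. The documents do not support that: nothing in them contradicts the fixed split, and choosing between two valid procedures is partly preference. This stands, and it sets the priority low.

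**The chance of a positive trial does not move.** A reader might infer that the fixed rule makes it harder to find a useful metabolite at all. It does not, because the first success is judged at 0.025 under both rules. Section II does not require success on both drugs, and VI.D sizes each comparison separately. The benefit is confined to the second drug. Section I.C treats the relative efficacy of the two as unknown, so equal effects of 0.62 SD are the favourable case.

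**The gain is not free.** A reader might infer that nothing is lost. When only one drug works, Holm raises false rejection of the inactive one from about 2.4% to 4.1%, with essentially no gain in power. A team choosing which drug to carry forward could prefer the stricter threshold. The trade-off is real, but 4.1% lies within the 5% that the plan already implies. Matching simultaneous confidence intervals are also simpler under the fixed split, though section VI plans none.

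**The absolute figures depend on the model.** VI.D expresses 0.62 SD on the global rank score, and VI.B ties all deaths at one rank and puts survivors on RRT in one category. Reading 0.62 as pooled rank SDs gives per-arm power of about 82% under the fixed rule and 87% under Holm. The levels shift, but the gain is again about 5 points.

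**Conclusion.** The point holds as an avoidable inefficiency. Holm can only add rejections, and it keeps the 5% family-wise bound under any dependence between the two comparisons. If both drugs have the planned effect, it adds about 5 points of power per arm and about 10 points for showing both. It adds about 9 points for the weaker drug when the effects are 0.62 and 0.31 SD, about 3 points per arm when both are 0.31 SD, and essentially nothing when one drug is inactive.

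The simulated figures assume a normal shift, no ties and a full 50 patients per arm. The dominance and the error bound need none of these assumptions, only that the family-wise level intended is 5%. Low priority.

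**What to change.** In VI.C, replace the fixed threshold with this text: *The two primary comparisons are tested by the Holm procedure at overall two-sided alpha 0.05: the smaller p value at 0.025 and, if significant, the other at 0.05.* This also puts the family-wise level in writing. VI.D can stand, with 2.5% as the conservative first-step alpha.

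The change must be made before unblinding. That is feasible: section IX.A leaves the assignment key with the research pharmacy throughout data collection, and IX.C says the primary end point is not assessed until the study is complete.

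The cost is one sentence, with no extra patients or data. The team should accept knowingly the higher false-rejection rate for an inactive arm beside an effective one. If it prefers the stricter per-drug threshold for that reason, one line in VI.C saying so would be enough.
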